3.1.2. Study Treatment

Avelumab (Arm A, Arm B) 10 mg/kg will be given as a 1-hour intravenous infusion (IV) every 2 weeks (Q2W) in 4-week cycles.

PLD (Arm B, Arm C) 40 mg/m² will be given as a 1-hour IV infusion every 4 weeks (Q4W) in 4-week cycles.

In Arm B, on the days that the patient receives both infusions, PLD should be administered prior to avelumab. See [Section 5.2.3.3](#).

In all patients, study treatment may continue until PD as assessed by the investigator, unacceptable toxicity, patient refusal, patient loss to follow up, or termination of the study by the Sponsor, whichever comes first (see [Section 6.5 Patient Withdrawal](#)). Avelumab and PLD will not be continued beyond initial disease progression. For those patients who are on single-agent avelumab post-progression at the time of amendment approval, if they present with a subsequent scan showing disease progression, they must discontinue avelumab. See [Section 5.2.4](#).

For administration information, see [Section 5.2.3](#). Patients should be monitored closely for toxicity and infusion related reactions. For the management of infusion-related reactions and other toxicities, see [Section 5.2.6](#).

Patients on Arm B who are discontinued from avelumab treatment for any reason, must also be discontinued from PLD (within the scope of this study, if applicable) and entered into the 90 Day Safety Follow-up Period.

Patients on Arm B who discontinue PLD for reasons other than disease progression may continue taking avelumab until withdrawal criteria are met.

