9.5. Safety Analysis

The Safety Analysis Set will be the primary population for safety evaluation. Summaries of AEs and other safety parameters will be provided by treatment arm as appropriate.

Adverse Events

Adverse events will be classified using the medical dictionary for regulatory activities (MedDRA) classification system. The severity of the toxicities will be graded according to the NCI CTCAE v4.03 whenever possible (<http://ctep.info.nih.gov/reporting/ctc.html>).

The frequency of patients experiencing treatment emergent adverse events corresponding to body systems and MedDRA preferred term will be reported. Adverse events will be graded by worst NCI CTCAE v4.03 Grade. Adverse events will be summarized by cycle and by relatedness to trial treatment.

Emphasis in the analysis will be placed on AEs classified as treatment emergent. Adverse events leading to death or discontinuation of trial treatment, events classified as NCI CTCAE v4.03 Grade 3 or higher, trial drug-related events, and serious adverse events will be considered with special attention. As appropriate, the difference in risk between treatment arms for AEs of clinical interest may be further assessed as described in the SAP.

Detailed information collected for each AE will include a description of the event, duration, whether the AE was serious, intensity, relationship to study treatment, action taken, and clinical outcome.

Laboratory Abnormalities

The laboratory results will be graded according to the NCI CTCAE v4.03 severity grade. The frequency of patients with laboratory test abnormalities will be summarized according to the worst grade for each laboratory test.

For laboratory tests without an NCI CTCAE grade definition results will be categorized as normal (within normal ranges), abnormal, or not done.

Shift tables will be provided to examine the distribution of laboratory abnormalities.

Electrocardiograms

ECG measurements (an average of the triplicate measurements) will be used for the statistical analysis and all data presentations. Single ECGs and data obtained from ECGs repeated for safety reasons after the nominal time-points will not be averaged along with the preceding triplicates. Interval measurements from repeated ECGs will be included in the outlier analysis (categorical analysis) as individual values obtained at unscheduled time points.

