3.5. Safety Endpoints

3.5.1. Adverse events

Treatment-Emergent Adverse Events

Treatment-emergent adverse events (TEAEs) are those events with onset dates occurring during the on-treatment period for the first time, or if the worsening of an event is during the on-treatment period.

On-treatment period is defined as the time from the first dose of study treatment through minimum (30 days + last dose of study treatment, start day of new anti-cancer drug therapy – 1 day). The start day of new anti-cancer drug therapy after the first dose of study treatment is derived as outlined in Section 5.2.5.

Adverse Events of Special Interest (AESIs)

AESIs are immune-related adverse events (irAE) and infusion-related reactions (IRRs). The criteria for classification of an AE as an irAE or IRR are described in Appendices 1 and 2, respectively.

3-Tier Adverse Events

It should be recognized that most studies are not designed to reliably demonstrate a causal relationship between the use of a pharmaceutical product and an adverse event or a group of adverse events. Except for select events in unique situations, studies do not employ formal adjudication procedures for the purpose of event classification. As such, safety analyses are generally considered as an exploratory analysis and its purpose is to generate hypotheses for further investigation. The 3-tier approach facilitates these exploratory analyses.

Adverse events and clusters of adverse events, of any causality and treatment-related, will also be summarized following a 3-tier approach. Under this approach, AEs are classified into 1 of 3 tiers.

Tier-1 events: These are pre-specified events or clusters of events of clinical importance and will be described in the Safety Review Plan.

Tier-2 events: These are events that are not Tier-1 but are “common”. A MedDRA PT is defined as a Tier-2 event if it is reported by

- a) at least 10% of patients with any grade in any treatment arm, or
- b) at least 5% of patients with Grade 3, 4 or 5 in any treatment arm.

Tier-3 events: All other AEs that are classified neither as Tier-1 nor Tier-2.

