For each of the two PFS comparisons, 325 PFS events by BICR assessment will provide 93% power to detect a HR of 0.6 using a 1-sided log rank test at a significance level of 0.001, and a 2-look group sequential design with Lan-DeMets (O'Brien-Fleming) α -spending function to determine the efficacy boundary and a Gamma Family (-10) β -spending function to determine the non-binding futility boundary.

The analysis cut-off date for the test of the 4 primary hypotheses for OS and PFS will be the same for the IA and, if applicable, for the final analysis. The hypotheses of TTD will be tested at the time of the primary OS and PFS analyses.

The sample size for this study is determined based on the assumptions that the median OS and PFS in control arm is 12 months and 3.5 months, respectively (Gordon et al, 2001; Colombo et al, 2012), and that treatment with avelumab alone or avelumab in combination with PLD is expected to increase the median OS and median PFS to ≥ 20 months and ≥ 5.8 months, respectively, corresponding to a hazard ratio (HR) of ≤ 0.6 under the exponential model assumption. The sample size further assumes a 5% drop-out rate for OS and 15% drop-out rate for PFS within each treatment arm and a non-uniform patient accrual over a 19-month period. The data cut-off for the primary OS and PFS analyses will occur after the target number of events for both endpoints has been reached within each comparison and the last patient randomized in the study has been followed for at least 12 months after randomization.

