5.2.7. Definition of on-treatment period

Safety endpoints will be summarized based on the on-treatment period unless otherwise specified.

On-treatment period is defined as the time from the first dose of study treatment through minimum (30 days + last dose of study treatment, start day of new anti-cancer drug therapy – 1 day).

Safety data collected outside the on-treatment period as described above will be listed and flagged in listings but will not be summarized.

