- **Infusion-related Reactions (IRR):** IRRs (as identified according to the methodology outlined in Appendix 2 for a pre-specified search list of MedDRA PTs documented in the

Safety Review Plan and finalized for analysis of the current studies data prior to DB lock).

Unless otherwise specified, AEs will be summarized by number and percentage of patients with the AE in the category of interest as described above, by treatment arm, primary SOC and PT in decreasing frequency based on the frequencies observed for the avelumab treatment arm (Arm A).

Each patient will be counted only once within each SOC or PT. If a patient experiences more than one AE within a SOC or PT for the same summary period, only the AE with the strongest relationship or the worst severity, as appropriate, will be included in the summaries of relationship and severity.

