6.6.4. Other significant adverse events

The frequency (number and percentage) of patients with each of the following will be presented for irAEs, by treatment arm:

- irAEs leading to death, by Cluster and PT
- irAEs, by Cluster and PT

- irAEs, Grade ≥ 3 , by Cluster and PT
- irAEs leading to discontinuation of avelumab, by Cluster and PT
- irAEs leading to discontinuation of PLD, by Cluster and PT
- irAEs leading to discontinuation of any study drug, by Cluster and PT
- irAEs leading to discontinuation of all study drugs, by Cluster and PT
- Serious irAEs, by Cluster and PT

The listing of all irAEs will also be provided with the relevant information with a flag for irAEs with onset outside of the on-treatment period.

The frequency (number and percentage) of patients with each of the following will be presented for IRRs, by treatment arm:

- IRRs leading to death, by PT
- IRRs, by PT
- IRRs, Grade ≥ 3 , by PT
- IRRs leading to discontinuation of avelumab, by PT
- IRRs leading to discontinuation of PLD, by PT
- IRRs leading to discontinuation of any study drug, by PT
- IRRs leading to discontinuation of all study drugs, by PT
- Serious IRRs, by PT
- Time related to first onset of an IRR (infusion 1, infusion 2, infusion 3, infusion 4 or later). For IV study drugs administered in combination the infusion numbers are those associated with the regimen, rather than the individual study drugs.

The listing of all IRRs will also be provided with the relevant information with a flag for IRRs with onset outside of the on-treatment period.

In addition, the following analyses will be presented for Tier-1 (irAEs and IRRs as defined in Appendices 1 and 2) and Tier-2 events separately. P-values and CIs for risk difference will be calculated based on the unconditional exact method by Santner and Snell (1980). No additional analyses will be presented for Tier-3 AEs.

- Frequency (number and percentage) of patients with each of the following by treatment arm and PT or Clustered Term:
 - Tier-2 AEs
 - Tier-2 AEs Grade ≥ 3

- Point estimate for risk difference and 95% CI for risk difference (experimental arm vs comparator arm) for each of the following by PT or Clustered Term:
 - irAEs
 - irAEs Grade ≥ 3
 - IRRs
 - IRRs Grade ≥ 3
 - Tier-2 AEs
 - Tier-2 AEs Grade ≥ 3
- 2-sided p-value associated with risk difference (experimental arm vs comparator arm) for each of the following by PT or Clustered Term:
 - irAEs
 - irAEs Grade ≥ 3
 - IRRs
 - IRRs Grade ≥ 3

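### SAP 6.6.4 compares arms on crude adverse-event percentages over windows that lengthen with treatment, and plans no fixed-time or exposure-based comparison beside them

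*SAP*

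**What the plan says.** SAP 6.6.1 sets the measure: "AEs will be summarized by number and percentage of patients with the AE in the category of interest". SAP 5.2.7 sets the period: "Safety endpoints will be summarized based on the on-treatment period unless otherwise specified". SAP 3.5.1 gives its length: "On-treatment period is defined as the time from the first dose of study treatment through minimum (30 days + last dose of study treatment", or the day before a new anti-cancer drug starts if that comes first. For irAEs, Appendix 1 (Table 16) instead counts onsets to 90 days after last dose, whether or not new therapy has begun.

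The between-arm analysis in SAP 6.6.4 is "Point estimate for risk difference and 95% CI for risk difference (experimental arm vs comparator arm", for irAEs, IRRs and Tier-2 events. Two-sided p-values are listed for irAEs and IRRs only. The method is stated: "P-values and CIs for risk difference will be calculated based on the unconditional exact method by Santner and Snell (1980".

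Under Protocol 3.1.2 treatment may continue to investigator-assessed progression, unacceptable toxicity, refusal, loss to follow-up or study termination. SAP 5.1.1 plans on avelumab being "expected to increase the median OS and median PFS to ≥ 20 months and ≥ 5.8 months, respectively", against 12 and 3.5 months on PLD.

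Exposure is tabulated separately (SAP 6.5.3.1 and 6.5.3.2). The one timing summary for adverse events is first IRR onset by infusion number. Protocol 9.5 states "Adverse events will be summarized by cycle and by relatedness to trial treatment", but SAP 6.6.1 to 6.6.4 list no by-cycle table.

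**The concern.** A secondary objective is the safety profile of each avelumab arm versus PLD alone. A patient observed longer has more time to have a first event. When window length differs by arm, a difference in crude percentages mixes toxicity with observation time, and nothing else in the plan separates the two.

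The windows can differ for three reasons:

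- **Efficacy.** The trial is sized on an arm difference in time to progression, the main planned reason for stopping.
- **Treatment rules.** In Arm B avelumab may go on after PLD stops, and the last dose is the later of the two drugs (SAP 3.4.1). Protocol 3.1.2 also shows that some patients had avelumab beyond progression: "For those patients who are on single-agent avelumab post-progression at the time of amendment approval".
- **Dosing interval.** Avelumab is given every 2 weeks and PLD every 4. A patient found to have progressed at the 8-week scan, before Cycle 3, had her last avelumab dose on Day 43 or her last PLD dose on Day 29. Her window ends on Day 73 or Day 59, a 14-day gap at identical progression.

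The distortion can go either way. A longer-treated arm looks more toxic than it is. An arm that stops sooner than PLD has its harm understated.

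**Working it through.** **The plan's own effect.** For PFS, with 325 events, HR 0.6 and one-sided 0.001, the fixed-sample approximation gives power Φ(|ln 0.6|·√(325/4) − 3.090) = Φ(4.605 − 3.090) = 0.935, against the stated 93%. For OS, with 196 events and one-sided 0.0115, it gives 0.904, against 90%. The ratio 3.5/5.8 is 0.603. The planned effect is reproduced.

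**Inputs.** Medians 3.5 and 5.8 months, exponential (SAP 5.1.1). Tail 30/30.4375 = 0.986 month, or 90/30.4375 = 2.957 months for irAEs. Patients per arm 550/3 ≈ 183. Assumed, because the documents give no figure: the adverse-event rate, its shape over time, and treatment stopped only at progression.

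**Mean window** = median/ln 2 + tail. Control: 5.05 + 0.99 = 6.04 months. Experimental: 8.37 + 0.99 = 9.35 months.

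**Event with the same constant hazard λ in both arms.** With h = ln 2/median (0.1980 and 0.1195 per month), crude incidence = 1 − exp(−λ·tail)·h/(h+λ). For 20% in control, λ = 0.0400. The experimental figure is then 1 − 0.961 × 0.1195/(0.1195 + 0.0400) = 27.9%.

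Chance that the 95% CI excludes 0, at 183 per arm:

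| Control | Experimental | Excess (points) | Exact | Normal approx. |
|---|---|---|---|---|
| 5% | 7.5% | 2.5 | 0.1% | 17% |
| 10% | 14.7% | 4.7 | 4% | 28% |
| 20% | 27.9% | 7.9 | 27% | 43% |
| 30% | 40.0% | 10.0 | 44% | 51% |
| 40% | 50.9% | 10.9 | 52% | 55% |

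The largest excess is 11.0 points. The exact column assumes that the Santner-Snell method orders tables by the raw difference. The interval then excludes 0 once the arms differ by at least 20 patients (20/183 = 10.9 points).

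**Variations on the 30-day window**

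- *Other reasons for stopping.* A common extra hazard of 0.05 or 0.10 per month, with λ re-solved for 20% in control, gives 25.6% or 24.2%, an excess of 5.6 or 4.2 points.
- *Front-loaded events.* With a Weibull shape of 0.5, 20% becomes 23.9% and 30% becomes 35.1%. With mean onset at 0.5 month the excess is about 0.1 point, and the flag rate is about the nominal 5%.
- *Reversed durations.* Protocol 1.2.2.4 reports a median PFS of 11.4 weeks (2.62 months) on avelumab in a heavily pretreated cohort. Against 3.5 months, the 20% event shows 16.5% on avelumab. An event with a hazard about 25% higher on avelumab would show equal percentages.

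**irAEs, 90-day window.** Control 10/20/30% gives an excess of 3.6/6.2/7.9 points. The flag rate is 2/16/29% (exact) or 19/29/36% (normal approximation).

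**IRRs.** These are tied to the infusion day or the day after (Appendix 2). In the pooled expansion cohort 30 + 16 = 46 of 49 patients had onset after infusion 1 or 2 (Protocol 1.2.2.2), so later follow-up adds little.

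**Would a person-time rate cure it?** In 4,000 simulated trials per scenario, comparing exposure-adjusted rates flagged the constant-hazard null event 3.7 to 5.4% of the time. For the early event (mean onset 0.5 month) it flagged 27 to 65%.

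**The case against.** The case for leaving the section alone has several parts.

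- **Purpose.** SAP 3.5.1 calls safety analyses generally exploratory, and 6.6.4 limits its p-values and CIs to screening and its CIs to estimation. No decision rule depends on them. This stands, and it limits the consequence. But the caveat in 6.6.4 concerns multiplicity and precision, not unequal follow-up, and an estimate used for screening is still better without a predictable bias.
- **A legitimate quantity.** Crude on-treatment incidence describes what a patient meets while on a regimen, and exposure by arm is tabulated elsewhere. This is a good reason to keep the crude tables. A separate duration table shows that windows differ, but not how much of a risk difference that explains.
- **The size is a scenario.** This stands. The model uses PFS by central review as a stand-in for treatment duration, which follows investigator progression and other reasons. It also omits the cap at new anti-cancer therapy. That omission does not inflate the excess if the cap shortens both tails alike: with no tail, λ = h/4 = 0.0495, and 20% becomes 0.0495/(0.1195 + 0.0495) = 29.3%.
- **The by-cycle table.** Protocol Section 9 lets the SAP modify protocol plans, so its absence is only a point to reconcile.

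A reader might infer that a harmless drug will generally show 8 points more of an event and often reach p < 0.05. The documents do not support that. The 8 points need 20% control incidence, a constant hazard and stopping only at progression. The 43% comes from a normal approximation, not the exact method in the SAP. The 30-day case fits Tier-2 events, which get no p-value. The events that do get one are irAEs, which are less affected (the avelumab ovarian cohort had 10.7%, Protocol 1.2.2.4), and IRRs, which are hardly affected.

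**Conclusion.** The point holds as a gap in the analysis that is cheap to close. The between-arm harm estimates in SAP 6.6.4 rest on windows whose length depends on arm, and no planned analysis puts the arms on a common time scale.

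At the planned PFS effect with the full 30-day tail, an event with equal hazard shows an excess of about 0 points (early onset) to 11 points (constant hazard, control incidence around 40 to 50%) in the experimental arm. At 20% and constant hazard it is about 8, or 4 to 6 with the added stopping hazards. At 20%, a Tier-2 interval excludes 0 about 27% of the time under the assumed exact method and 43% under the normal approximation.

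A reader might also infer that the safety results are wrong in a known direction. That does not follow. Protocol Section 9 records that the primary objectives were not met, and the documents give no actual treatment durations. Either direction is possible, including understated harm.

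**What to change.** Keep the crude tables and risk differences. Add to SAP 6.6.4, for irAEs and Tier-2 events, the between-arm difference with 95% CI in cumulative incidence of first event at fixed times, for example 8 and 16 weeks. Treat death before the event as a competing event, and censor patients without the event at the end of their window. Report exposure-adjusted rates only as support, because they mislead for front-loaded events. Either add the by-cycle summary of Protocol 9.5 or state that it has been dropped.

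Enough patients should remain under observation. In the same model, the share still in the 30-day window at 16 weeks (3.68 months) is exp(−0.198 × 2.69) = 59% in control and exp(−0.1195 × 2.69) = 72% in the experimental arm.

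The cost is a few tables from dates already collected. The drawback is that censoring at the end of the window is assumed non-informative, which may fail if event risk is linked to progression; the SAP should say so. Since Protocol Section 9 records the final analysis as complete, tables added now should be labelled as added after it.

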6.6.5. Laboratory data

6.6.5.1. Hematology and chemistry parameters

Laboratory results will be classified according to the NCI-CTCAE criteria version 4.03. Non-numerical qualifiers (with the exception of fasting flags) will not be taken into consideration in the derivation of CTCAE criteria (eg, hypokalemia Grade 1 and Grade 2 are only distinguished by a non-numerical qualifier and therefore Grade 2 will not be derived). Additional laboratory results that are not part of NCI-CTCAE will be presented according to the categories: below normal limit, within normal limits and above normal limit (according to the laboratory normal ranges).

Quantitative data will be summarized using simple descriptive statistics (mean, SD, median, Q1, Q3, minimum, and maximum) of actual values and changes from baseline for each nominal visit over time (unscheduled measurements would therefore not be included in these summaries as described in Section 5.2.9). End of Treatment visit laboratory results will be summarized separately. The changes computed will be the differences from baseline. Qualitative data based on reference ranges will be described according to the categories (ie, Low, Normal, High).

Abnormalities classified according to NCI-CTCAE toxicity grading version 4.03 will be described using the worst grade. For those parameters which are graded with two toxicities

such as potassium (hypokalemia/hyperkalemia), the toxicities will be summarized separately. Low direction toxicity (eg, hypokalemia) grades at baseline and post baseline will be set to 0 when the variables are derived for summarizing high direction toxicity (eg, hyperkalemia), and vice versa.

For **WBC differential counts** (total neutrophil [including bands], lymphocyte, monocyte, eosinophil, and basophil counts), the absolute value will be used when reported. When only percentages are available (this is mainly important for neutrophils and lymphocytes, because the CTCAE grading is based on the absolute counts), the absolute value is derived as follows:

$$\text{Derived differential absolute count} = (\text{WBC count}) \times (\text{Differential \%value} / 100)$$

If the range for the differential absolute count is not available (only range for value in % is available) then Grade 1 will be attributed to as follows:

- Lymphocyte count decreased:
 - derived absolute count does not meet Grade 2-4 criteria, and
 - % value < % LLN value, and
 - derived absolute count $\geq 800/\text{mm}^3$
- Neutrophil count decreased
 - derived absolute count does not meet Grade 2-4 criteria, and
 - % value < % LLN value, and
 - derived absolute count $\geq 1500/\text{mm}^3$

For **calcium**, CTCAE grading is based on Corrected Calcium and Ionized Calcium (CALCIO). Corrected Calcium is calculated from Albumin and Calcium as follows

$$\text{Corrected calcium (mmol/L)} = \text{measured total Calcium (mmol/L)} + 0.02 (40 - \text{serum albumin [g/L]})$$

Liver function tests: Alanine aminotransferase (ALT), aspartate aminotransferase (AST), and total bilirubin (TBILI) are used to assess possible drug induced liver toxicity. The ratios of test result over upper limit of normal (ULN) will be calculated and classified for these three parameters during the on-treatment period.

Summary of liver function tests will include the following categories. The number and percentage of patients with each of the following during the on-treatment period will be summarized by treatment arm:

- ALT $\geq 3 \times \text{ULN}$, ALT $\geq 5 \times \text{ULN}$, ALT $\geq 10 \times \text{ULN}$, ALT $\geq 20 \times \text{ULN}$
- AST $\geq 3 \times \text{ULN}$, AST $\geq 5 \times \text{ULN}$, AST $\geq 10 \times \text{ULN}$, AST $\geq 20 \times \text{ULN}$

- (ALT or AST) $\geq 3 \times \text{ULN}$, (ALT or AST) $\geq 5 \times \text{ULN}$, (ALT or AST) $\geq 10 \times \text{ULN}$, (ALT or AST) $\geq 20 \times \text{ULN}$
- TBILI $\geq 2 \times \text{ULN}$
- Concurrent ALT $\geq 3 \times \text{ULN}$ and TBILI $\geq 2 \times \text{ULN}$
- Concurrent AST $\geq 3 \times \text{ULN}$ and TBILI $\geq 2 \times \text{ULN}$
- Concurrent (ALT or AST) $\geq 3 \times \text{ULN}$ and TBILI $\geq 2 \times \text{ULN}$
- Concurrent (ALT or AST) $\geq 3 \times \text{ULN}$ and TBILI $\geq 2 \times \text{ULN}$ and ALP $> 2 \times \text{ULN}$
- Concurrent (ALT or AST) $\geq 3 \times \text{ULN}$ and TBILI $\geq 2 \times \text{ULN}$ and (ALP $\leq 2 \times \text{ULN}$ or missing)

Concurrent measurements are those occurring on the same date.

Categories will be cumulative, ie, a patient with an elevation of AST $\geq 10 \times \text{ULN}$ will also appear in the categories $\geq 5 \times \text{ULN}$ and $\geq 3 \times \text{ULN}$. Liver function elevation and possible Hy's Law cases will be summarized using frequency counts and percentages.

An evaluation of Drug-Induced Serious Hepatotoxicity (eDISH) plot will also be created, with different symbols for different treatment arms, by graphically displaying

- peak serum ALT(/ULN) vs peak total bilirubin (/ULN) including reference lines at ALT=3 \times ULN and total bilirubin=2 \times ULN.
- peak serum AST(/ULN) vs peak total bilirubin (/ULN) including reference lines at AST=3 \times ULN and total bilirubin=2 \times ULN.

In addition, a listing of all TBILI, ALT, AST and ALP values for patients with a post-baseline TBILI $\geq 2 \times \text{ULN}$, ALT $\geq 3 \times \text{ULN}$ or AST $\geq 3 \times \text{ULN}$ will be provided.

Parameters with NCI-CTC grades available:

The laboratory toxicities will be tabulated using descriptive statistics (number of patients and percentages) during the on-treatment period. The denominator to calculate percentages for each laboratory parameter is the number of patients evaluable for CTCAE grading (ie those patients for whom a Grade 0, 1, 2, 3 or 4 can be derived).

- The summary of laboratory parameters by CTCAE grade table will include number and percentage of patients with Grade 1, 2, 3, 4, Grade 3/4 and any grade (Grades 1-4), laboratory abnormalities during the on-treatment period.
- The shift table will summarize baseline CTCAE grade versus the worst on-treatment CTCAE grade. The highest CTCAE grade during the on-treatment period is considered as the worst grade for the summary.

The above analyses apply to hematology and chemistry evaluations which can be graded per CTCAE, ie:

- Hematology:

Hemoglobin (HB), Leukocytes (white blood cell decreased), Lymphocytes (lymphocyte count increased/decreased), Neutrophils / Absolute Neutrophils Count (ANC) (neutrophil count decreased), Platelet Count (PLT) (platelet count decreased).

- Serum Chemistry:

Albumin (hypoalbuminemia), Alkaline Phosphatase (alkaline phosphatase increased), Alanine Aminotransferase (ALT) (ALT increased), Amylase (serum amylase increased), Aspartate Aminotransferase (AST) (AST increased), Total Bilirubin (blood bilirubin increased), Cholesterol (cholesterol high), Creatinine (creatinine increased), Creatine Kinase (CPK increased), Potassium (hypokalemia/ hyperkalemia), Sodium (hyponatremia/ hypernatremia), Magnesium (hypomagnesemia/hpermagnesemia), Calcium (hypocalcemia/ hypercalcemia), Glucose (hypoglycemia/hyperglycemia), Gamma Glutamyl Transferase (GGT) (GGT increased), Lipase (lipase increased), Phosphates (hypophosphatemia), Triglycerides (hypertriglyceridemia).

Parameters with NCI-CTC grades not available:

Hematology and chemistry evaluations which cannot be graded per CTCAE criteria will be summarized as frequency (number and percentage) of patients with:

- shifts from baseline normal to at least one result above normal during on-treatment period
- shifts from baseline normal to at least one result below normal during on-treatment period

In this study, these apply to the following parameters:

- Hematology: Absolute Monocytes, Absolute Eosinophils, Absolute Basophils
- Serum Chemistry: Chloride, Total Urea, Uric Acid, Total Protein, C-Reactive Protein, Lactate Dehydrogenase (LDH)

